3.1. Study Population

This intervention is offered to significant caregivers of a child between the ages of 3 and 18 who have questions about the support a child needs when confronted with a parent's cancer. In this study, the term "significant caregiver" refers to any person who provides significant practical, educational and emotional care to the child.

In order to respond to the heterogeneity of family and medical situations, each significant caregiver may decide to participate in the intervention alone or accompanied by a relative involved in the child's support.

The inclusion criteria for each participant are as follows:

- Participants must be of legal age (at least 18 years old);
- Participants must not have an acute psychiatric or neurological disorder that does not allow them to participate to the study and the intervention;
- Participants must have a sufficient command of French (speaking, writing and reading).

Participants cannot be included if:

- The child's parent with cancer is in a pre-terminal or terminal phase;
- The child's parent with cancer has died.

The sample size was calculated a priori to detect differences in the evolution of the two groups ("control" condition and "experimental" condition) between T1 and T2. A pilot study suggests a minimum expected effect size of 0.8 (effect size) if the GC remains stable. Under this double assumption, an overall population of 68 subjects (34 subjects in each group) will be required to achieve a level of significance (p) of 5% with a statistical power of 90%.

However, taking into account possible dropouts, the total recruitment sample should be 80 participants.

Regarding recruitment, as soon as a patient is identified by the team as having a child between 3 and 18 years of age, he or she is contacted to suggest the project. Information to identify and contact patients is taken from medical records. One study found that following or having recently followed chemotherapy or radiation therapy was associated with a higher level of

parental competence (Moore, 2015). In this way, a more systematic recruitment will be organised within the Jules Bordet Institute at the day hospital and in radiotherapy in agreement with the department heads. In addition, in order to facilitate families' access to the project, the study is being disseminated to front-line carers (doctors, nurses, psychologists, social workers, NOC, etc.) within the Jules Bordet Institute, Erasmus Hospital and also in other hospitals via the distribution of information sheets and oral presentations.

3.2. Description of the study.

This is a randomized longitudinal controlled study conducted at the Jules Bordet Institute site and at Erasmus Hospital (Figure 1). This study evaluates the effectiveness of a psychological intervention focused on helping children in the oncology context. Significant caregivers may participate alone or in dyads at the intervention. At the time of recruitment (T0), after checking the eligibility criteria, participants receive all the information associated with the study. As a first step, they are offered the opportunity to perform the dyad intervention. If this is not possible, participants have the opportunity to participate in an individual way. After this step of presenting the information, they sign a consent form for inclusion in the study. As soon as they are included, the participants (in dyads or individually) have a first evaluation time (T1) consisting of the completion of questionnaires and a semi-directive interview.

[figure not shown]
At the end of T1, all participants (experimental condition and control condition) receive an information booklet entitled "How to talk with the child about a parental cancer? A practical booklet on communication. "[23] which contains parental information and recommendations associated with supporting a child facing a parent's cancer.

After T1, each participant is directly randomly assigned to either the experimental or control condition. Randomization is done after the first evaluation so that evaluators and participants are not aware of the distribution at T1.

After receiving the information booklet, participants randomized to the experimental condition receive a brief parental support intervention consisting of four sessions. Fifteen days after the end of the intervention, these participants have a second evaluation (T2), again consisting of the completion of questionnaires and a semi-directive interview.

After receiving the information booklet, randomized participants in the control condition are placed on a waiting list. Nine weeks after the end of T1, these participants have a second evaluation time (T2) consisting of the completion of questionnaires and a semi-directive interview. They subsequently benefit from parental support intervention.

The entire study was manualized and standardized in order to best meet the methodological recommendations recommended by "CONSORT"[18].

Information booklet: "How to talk to your child about a parental cancer? A practical booklet on communication. » [23]

All participants (control and experimental conditions) receive an information booklet containing parental information and recommendations associated with supporting a child facing a parent's cancer. To address this theme, the booklet describes concepts related to child

development such as understanding the disease, reactions and needs. It also presents recommendations related to communication around the disease according to the child's age and development (*what to say to the child?* and *how to respond to the child?*). Finally, the booklet offers resources (e.g., books, websites, non-profit organisations) that are useful in this context.

3.3. Parental Support Intervention.

3.3.1. Objectives of the intervention.

While the information booklet mainly aims to increase the knowledge of significant caregivers about supporting a child facing a parent's cancer, the parental support intervention aims to develop and reinforce their behaviors associated with supporting the child in this context. The intervention aims to improve communication with the child by strengthening the sense of communicative competence and transmitting emotional regulation strategies. The dyad intervention also aims to strengthen mutual support between participants.

3.3.2. Content of the intervention.

This is a brief four-session parental support psychological intervention that can be done individually or in a dyad. The first session is dedicated to a global assessment of the medical and family situation, communication with the child, as well as to an identification and reinforcement of the participant's parental skills. The second session suggests to the participant to identify the reactions and needs of children in the context of the disease and based on concrete examples. A construction work of what can influence perception is carried out. The last two sessions are devoted to the participant's specific questions about communicating with his or her children in the context of the disease.

In general, emotional regulation techniques specific to parenthood are worked on during the session and reinforced by the transmission of a relaxation booklet. Parental competence is systematically supported and strengthened. The content does not change whether one is in a dyadic or individual intervention except that dyadic interactions and support are enhanced.

Our workers are trained in the management of families through their clinical practice within the activities of "Bordet'N Family". In order to increase the fidelity of intervention replication, future practitioners will also benefit from a training process that involves three stages: general theoretical training in intervention, practical training specific to the intervention and

supervisions scheduled after each session with an experienced psychologist. In addition, the workers are supervised by the study coordinator ([name]).

A quality control of the intervention is set up by an audio and video recording of the interventions. These records are regularly analyzed using an analysis grid created from the intervention manual to verify the standardization of the intervention.

3.4. Evaluation procedure and questionnaires.

This study includes 2 evaluation periods, T1 and T2, consisting of the completion of questionnaires and a semi-directive individual interview. The evaluation procedure includes a research interview which is structured in three parts. The entire research interview lasts approximately 1h30.

The first part focuses on supporting the child facing a parent's cancer. To do this, participants are asked to complete several questionnaires with specific reference to only one child in their circle. This child must face a parent's cancer and must be between 3 and 18 years old. If several children meet these criteria, the participant determines the one for whom he or she has the most questions about how to communicate with him or her about the disease. When it comes to dyads, participants agree on the choice of the child. The child identified serves as a reference during both T1 and T2 in order to standardize the assessment procedure as much as possible. Participants are invited to complete questionnaires describing the situation of the identified child, as well as questionnaires focusing on their parental concern and support for the child.

- Individual intervention:
 - The socio-demographic data of the identified child.
 - The relationship of the participant(s) to the identified child.
 - The medical context of the disease. Two versions of this questionnaire were created for the study: one for non-patient participants and one for sick participants.
 - The sense of communicative competence. A questionnaire developed specifically for the study was created from the theories of parental competence in oncology and self-efficacy theories[13-15, 19].
 - Communication with the child. The participant's communication with the child is assessed by a questionnaire specifically developed for the study. This questionnaire contains two

subscales: communication with the child and the emotional regulation associated with this communication.

- Concerns about the identified child. An adaptation of Muriel et al.'s Parenting Concerns Questionnaire (PCQ)[2] was developed for the study. Since the PCQ is an oncology patient questionnaire, one item has been removed so that all items can be adapted to all participants.
- The feeling of knowledge. The participants' sense of knowledge about the support to the identified child is assessed by a questionnaire specifically developed for the study. This questionnaire was created from the concepts developed in the information booklet.

- Dyad intervention:

- idem plus two questionnaires, the first evaluating the relationship with the person who supports them in relation to the child and the second evaluating the mutual support between the participants by means of a questionnaire specifically developed for the study.

The second part of the evaluation is a semi-directive interview with the researcher. Each participant will individually answer a serie of questions about communicating with the identified child. The semi-directive interview consists of a framework of open and semi-open questions structured around predefined themes concerning communication with the identified child: general communication with the child, the emotions aroused during these exchanges, the child's reactions, the elements facilitating and disrupting communication. The semi-directive interview is audibly recorded and transcribed.

The third part of the evaluation consists of the completion of questionnaires to collect a serie of descriptive information from participants:

- The socio-demographic data of the participant.
- The psychological background of the participant.
- The social difficulties of the participant. Social difficulties are assessed using the Social Difficulties Inventory (SDI-16)[20].
- The emotional state of the participant. Emotional state is assessed using the Hospital Anxiety and Depression Scale (HADS)[21];
- The emotional state of the identified child. The emotional state of the identified child is assessed using the Child Behavior Check List (CBCL)[22]. Two versions adapted to the age of the identified child are used: one for children between 3 and 5 years old and the other for children between 6 and 18 years old.

- Knowledge about children's understanding of the disease. Participants' level of knowledge about children's understanding of the disease is assessed using a questionnaire specifically designed for the study.

At T2, the evaluation procedure is similar to the one mentioned above. In addition, the use and relevance of the information booklet and the satisfaction with the intervention of participants of the experimental condition are assessed.

3.5. Statistical analysis.

Before evaluating the effectiveness of the parental support intervention, the data will be examined to verify sample distributions and outliers. In addition, control analyses will be carried out to compare participants of experimental conditions and controls during T1 and to compare participants who performed T1 and T2 and those who dropped out (T1 completed). A comparative analysis between the group that performed the dyad intervention and the group that performed the intervention individually will be conducted in order to identify any differences in profile. An analysis using a mixed linear model including random effects will be used to compare the evolution of participants from the experimental condition to the control condition and consequently test the effectiveness of the intervention. This analysis will be done separately for participants who performed the intervention individually and those who did it in dyads. As for the content of the semi-directive interviews, a content analysis will be carried out.

4. Ethical and regulatory aspects.

This study does not present any risk to the physical health of the participants. Only questionnaires (T1-T2 assessment procedures) and interviews (during the T1- T2 assessment procedures and parental support intervention) are used. No biological sampling is carried out.

Participation in the study does not exclude the possibility of benefiting from traditional psycho-social care. During the study, if significant emotional distress is observed in one of the participants, appropriate management will be offered. In addition, if the child's caregiver with cancer dies during the study, participants will be able to benefit from specific care.

Concerning recruitment, the psychologists who suggest the intervention have been made aware of the study. The team of workers and interviewers is composed of psychologists and

doctors of psychology trained in the specific clinical aspects of psycho-oncology and family management.

Participation in the study is voluntary and participants may decide at any time to terminate their participation without affecting the quality of their medical and psychosocial care. Participants are informed of the entire research project since the study does not require blind conduct. This information is included in the document "Information letter and informed consent of the participant" given to each participant. No remuneration is required to participate to the study, participants benefit from free access to the study. Participants in the control group are notified that they are receiving parental support intervention after the second evaluation time. Before inclusion in the study, they are asked for their free and informed consent in writing.

All data collected is encrypted and stored on hard disks not connected to the Internet and themselves encrypted. The anonymity of the participants is guaranteed by a codification of their identity. The correspondence file between the code and the identity of the participants is stored separately from the database. Access to these external hard disks is only possible to trusted persons who are part of the research team. The principal investigator guarantees that anonymity and confidentiality are strictly respected throughout the project.

5. Bibliographie

1. Fondation Registre du Cancer. (n.d.). Les chiffres du cancer. Retrieved from http://www.kankerregister.org/Les_chiffres_du_cancer
4. Osborn, T. (2007). The psychosocial impact of parental cancer on children and adolescents: a systematic review. *Psycho-Oncology*, 16(2), 101–126. doi:10.1002/pon.1113
5. Compas, B. E., Worsham, N. L., Ey, S., & Howell, D. C. (1996). When mom or dad has cancer: II. Coping, cognitive appraisals, and psychological distress in children of cancer patients. *Health psychology*, 15(3), 167–175.

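### Nothing limits enrolment to one unit per child or family, so two caregivers of one child who enter separately can be randomised to opposite arms; the likely loss is small and the remedy is one line

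*Protocol*

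**What the plan says.** Section 3.1 of the protocol sets a broad definition: "the term 'significant caregiver' refers to any person who provides significant practical, educational and emotional care to the child". Several people can meet it for one child, and section 1 says the intervention is meant for divorced, reconstituted and extended families. Section 3.1 also leaves the mode of participation to the individual: "each significant caregiver may decide to participate in the intervention alone or accompanied by a relative involved in the child's support".

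The inclusion criteria in 3.1 cover age, psychiatric or neurological disorder, and command of French. The two exclusions both concern the ill parent: death, and the condition "The child's parent with cancer is in a pre-terminal or terminal phase". Neither list mentions another caregiver of the same child.

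Section 3.2 offers the dyad first, with a fallback: "If this is not possible, participants have the opportunity to participate in an individual way". Allocation follows the first evaluation: "After T1, each participant is directly randomly assigned to either the experimental or control condition". No passage says that caregivers of one child who enter separately share an allocation. Controls receive the information booklet and wait, with T2 nine weeks after T1. The sample size in 3.1 is conditional on the control group remaining stable.

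**The concern.** Taken together, these provisions let a mother and a father, or a parent and a grandparent, enter as two individual participants for the same child and be allocated independently. If one is treated and the other is a control, the control may be partly exposed before T2.

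The protocol's own rationale makes this plausible. Section 1 describes parental cancer as calling for new behaviours that the parents put into practice together. The sessions teach communication and emotional regulation, and section 3.3.2 says the regulation techniques are "reinforced by the transmission of a relaxation booklet", which is easily shared. The outcome is the caregiver's communication with a child, and a treated co-caregiver may change how that child talks about the illness.

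The direction of the bias is predictable: improvement among exposed controls shrinks the difference between arms. It also strains the stable-control assumption behind the sample size. Analysis cannot recover what an exposed control would have reported without exposure, so the remedy belongs in eligibility or allocation.

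**Working it through.** **Inputs from section 3.1.** Effect size 0.8; significance level 5% (sidedness not stated); power 90%; 34 per group, 68 in total; 80 recruited.

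**Inputs assumed, because the documents give none.** Independent 1:1 allocation; k pairs of separately enrolled caregivers of one child among the 80; a fraction f of the treatment benefit reaching an exposed control, taken as 0.5.

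**Step 1: reproduce the plan's figure.** A two-sided two-sample t-test at 5% with d = 0.8 and 90% power needs 33.83 per arm, so 34 per arm and 68 in total. Power at 34 per arm is 0.902. A one-sided 5% test would need only about 27 per arm, so the plan's figure is two-sided. 68 / (1 − 0.15) = 80, so the recruitment target matches 15% dropout. The sample-size arithmetic is sound.

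**Step 2: chance that a pair is split.** Under independent 1:1 allocation this is 0.5. Each split pair yields one exposed control, so the expected share of exposed controls among 40 is c = 0.5k / 40.

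**Step 3: dilution.** The diluted effect is d = 0.8 × (1 − c × f), with power then read from the t-test at 34 per arm. At f = 0.5:

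| Pairs k | Exposed controls c | Dilution c × f | d | Power |
|---|---|---|---|---|
| 0 | 0 | 0 | 0.800 | 0.902 |
| 1 | 0.5/40 = 1.25% | 0.625% | 0.795 | 0.898 |
| 2 | 1/40 = 2.5% | 1.25% | 0.790 | 0.894 |
| 4 | 2/40 = 5% | 2.5% | 0.780 | 0.887 |
| 8 | 4/40 = 10% | 5% | 0.760 | 0.870 |
| 16 | 8/40 = 20% | 10% | 0.720 | 0.833 |

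**Step 4: what a large loss would require.** Power of 0.83 corresponds to 10% dilution. At half uptake that means 8 of 40 controls exposed, hence about 16 separately enrolled pairs, or 32 of the 80 participants (40%). Even at full uptake (f = 1) it would take 8 pairs, or 16 of 80.

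**Step 5: the individual track.** Section 3.5 analyses individual and dyad participants separately, so the same pairs weigh more in the individual-track comparison. Its size is not stated. If 40 of the 80 entered individually (assumption), four pairs would give 2 exposed controls of 20, or 10%. At half uptake that is 5% dilution and d = 0.76. The powers in the table use the plan's overall 34 per arm and are not powers for that track.

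**The case against.** The strongest reply is that the protocol never says two caregivers of one child will be enrolled or allocated separately; the point rests on a missing line. Section 3.2 offers the dyad first, and recruitment under 3.1 starts from the patient, so a second caregiver would normally enter as the accompanying relative. The figure in 3.2 is not shown and might state the unit of allocation. Section 3.2 also speaks of each participant without separating out dyads, so that wording is weak evidence on the unit. Exposure may be slight: the intervention is four psychologist-led sessions aimed at the participant's own competence, and a relative's attendance is not the same as receiving it.

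Much of this stands, but it bears on how often and how strongly the problem would occur, not on whether the route is open. Section 3.1 gives the choice of mode to each caregiver, the fallback in 3.2 exists for those who cannot attend together, and the study is publicised through front-line carers in several hospitals, so a second caregiver can arrive later by another path.

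Three stronger readings are tempting and are not supported:

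- **A serious loss of power.** A fall to 0.83 needs about 16 separately enrolled pairs at half uptake. Nothing in the documents suggests that, and the dyad-first offer makes it unlikely.
- **Wrong standard errors from related individuals.** Under independent allocation about half the pairs are split, where ignoring the correlation overstates the standard error. About half fall in the same arm, where it understates it. These offset in expectation. Section 3.5 also plans a mixed model whose random effects it does not name.
- **Exposure in a shared home, with the same reference child.** Separated parents are an obvious group unable to form a dyad, so exposure would run through co-parenting or the child. Under section 3.4 only dyads must agree on the reference child; two individual participants could choose different siblings.

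**Conclusion.** The gap is real but of low to moderate consequence. As written, the protocol allows separately enrolled caregivers of one child to be allocated to opposite arms, and the resulting bias is toward no effect. With an assumed 1 to 4 pairs among 80 and half uptake, the effect falls by about 0.6% to 2.5% and power from 0.90 to no lower than about 0.89. The weight is greater within the separately analysed individual track, by an amount that the documents do not allow one to fix. Pair frequency and uptake are both assumptions. The stated sample size is not in error. The case for acting is that prevention is cheap and later correction is not possible.

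**What to change.** Add to the criteria in section 3.1: *Only one enrolment unit (one individual or one dyad) per child/family is randomised; a later caregiver from the same family is not randomised separately and is not counted in the efficacy analysis.* Add one screening question at T0 asking whether another caregiver of the child is already enrolled. A later caregiver can still be offered the intervention outside the efficacy analysis.

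The cost is one line, one question and the loss of a few second caregivers from the 80. The calculated sample size of 68 does not change.

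### The 90% power is for one pooled comparison of 68 independent subjects, but the protocol describes only separate efficacy analyses for individuals and for dyads, and neither reaches 90% at that size

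*Protocol*

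**What the plan says.** **Sample size (Protocol, Section 3.1).** The trial is sized to detect a difference between the two conditions in their change from T1 to T2. The effect size of 0.8 comes from a pilot study, with the control group assumed stable. The result is "an overall population of 68 subjects (34 subjects in each group"), needed "to achieve a level of significance (p) of 5% with a statistical power of 90" per cent. The only inflation follows: "However, taking into account possible dropouts, the total recruitment sample should be 80 participants". No share of participants in dyads and no within-dyad correlation is given.

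**Formats and allocation (Sections 3.2, 3.3.1 and 3.4).** Caregivers take part alone or in pairs, and the pair is the preferred format: "As a first step, they are offered the opportunity to perform the dyad intervention". The pair exists before randomisation, because the T1 evaluation is already done in dyads or individually. Both members agree on one reference child. The sessions are joint: "The dyad intervention also aims to strengthen mutual support between participants". Controls wait and receive the intervention only after T2. The allocation sentence reads: "After T1, each participant is directly randomly assigned to either the experimental or control condition".

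**Analysis (Section 3.5).** A linear mixed model with random effects compares the evolution of the two conditions, and then: "This analysis will be done separately for participants who performed the intervention individually and those who did it in dyads". No comparison that combines the two formats is described.

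**The concern.** Section 3.1 gives the power of one comparison in the whole sample. Section 3.5 describes two comparisons, each in part of the sample. The 90% is the only power statement in the protocol, so it will be read as applying to the efficacy tests actually planned, and it does not. A null result in either format could then be taken as evidence from a 90%-powered test when the real figure may be nearer 50 to 60%.

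Two lesser matters sit beside this. First, the sample size counts persons as independent, although two caregivers of the same child who attend the same sessions may well change together. Secondly, the allocation sentence names the individual participant, whereas the joint intervention only works if the dyad is allocated as one unit.

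**Working it through.** **Inputs.** From Section 3.1: effect size d = 0.8, significance level 5%, 34 per arm, 68 in all, 80 recruited. Sidedness is not stated; two-sided reproduces the plan's number. Assumptions, because the protocol gives neither: the share of participants in dyads, and the ICC of the T1 to T2 change within a dyad, taken as 0.1 / 0.3 / 0.5 and equal in both arms.

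**Formula.** Power from the noncentral t distribution with noncentrality d × √(n/2), where n is the effective number per arm. For participants in dyads, n is divided by 1 + ICC (clusters of two). A dyad-only analysis has degrees of freedom equal to the number of dyads minus 2.

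**Step 1: reproduce the plan's figure.**
- 34 per arm: 0.8 × √17 = 3.298, df 66, power 90.2%.
- 33 per arm: 0.8 × √16.5 = 3.250, df 64, power 89.3%.

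So 34 per arm is the smallest independent-subjects size that gives 90%. The 80 corresponds to 68/0.85, an implied dropout of 15%.

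**Step 2: the separate analyses of Section 3.5 with 68 evaluable.** If at least one dyad is present in each arm, at most 32 single participants per arm remain: 0.8 × √16 = 3.2, df 62, power 88.3%. If two singles are present in each arm, at most 16 dyads per arm remain; at ICC 0 the noncentrality is again 3.2, df 30, power 87.2%. These are the best cases. Other splits per arm:

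| Split per arm | Individuals | Dyads, ICC 0.1 / 0.3 / 0.5 |
|---|---|---|
| Even, 17 persons in each format | 61.9% | 54.8 / 48.2 / 43.0% |
| 26 singles + 4 dyads | 80.7% | 25.2 / 22.1 / 19.8% |
| 8 singles + 13 dyads | 32.0% | 75.1 / 68.0 / 61.8% |

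In the even split, individuals have noncentrality 0.8 × √8.5 = 2.332 with df 32. The dyad row uses a nominal 8.5 dyads per arm, df 15, and gives 58.8% at ICC 0. With whole dyads, ICC 0 / 0.1 / 0.3 / 0.5:
- 8 dyads per arm: 55.8 / 51.9 / 45.6 / 40.6%.
- 9 dyads per arm: 61.6 / 57.5 / 50.7 / 45.3%.

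The split itself therefore costs 90.2 − 61.9 = 28.3 points for individuals and 90.2 − 58.8 = 31.4 for dyads. The ICC adds a further 58.8 − 54.8 = 4.0 to 58.8 − 43.0 = 15.8 points for dyads.

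**Step 3: a pooled comparison of the 68.** Effective n per arm = 34(1 − p) + 34p/(1 + ICC), with p the share of participants in dyads.
- p = 0.5: n = 32.5 / 30.1 / 28.3, power 88.7 / 86.2 / 84.1%.
- p = 1: n = 30.9 / 26.2 / 22.7, power 86.2 / 80.1 / 74.3% with df 32 (34 dyads minus 2).

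**Step 4: if all 80 recruited were evaluable, evenly split.** Pooled: 93.2 / 91.3 / 89.6%. Separate: 69.3% for individuals (20 per arm) and 62.6 / 55.6 / 49.8% for dyads (10 per arm).

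**The case against.** **The allocation sentence is only loose wording.** This stands. A reader might infer from it that members of a dyad could be sent to different arms. The protocol does not support that: pairs are formed before T1, treated jointly, and compared with a waiting list. Figure 1 is not available in the text at hand and may name the unit. Correcting the sentence would not change the 68 or the 90%.

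**The ICC is unknown.** This also stands. What matters is the correlation of change, and stable influences shared by the two members cancel in a change score. Control dyads receive only the booklet before T2, so one common ICC in both arms is an assumption. A negative correlation would raise power. The main point does not depend on this, because the split alone takes power below 90% at an ICC of 0.

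**The mixed model deals with clustering.** A reader might infer that the planned test has an inflated error rate. That cannot be charged: Section 3.5 plans random effects, and the level may be specified in an analysis plan not shown. A dyad-level effect would correct the standard error, but it would not restore the power stated in Section 3.1.

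**The 80 recruited give a margin.** They help only if dropout is well below the implied 15%. With 80 evaluable, 34 singles plus 3 dyads per arm (34 + 6 = 40) would give the individual analysis its 90.2%. The statement that neither analysis reaches 90% is therefore limited to 68 evaluable.

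**Conclusion.** The concern holds as a mismatch between Sections 3.1 and 3.5, and it should be fixed. The sample-size arithmetic is right for its own inputs, but the 90% belongs to a pooled comparison of independent subjects that the analysis section does not contain. With 68 evaluable, equal arms, both formats present and an ICC of 0 or above, neither separate analysis reaches 90%. With an even split the figures are about 62% for individuals and 59% for dyads, falling to 55 / 48 / 43% over the assumed ICC range. Most of the loss comes from the split.

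The lack of any allowance for positive within-dyad correlation is secondary. For a pooled comparison it costs little with half in dyads (89 / 86 / 84%) and is larger only if everyone is in a dyad (86 / 80 / 74%). A reader might infer that clustering alone leaves the trial badly underpowered; the protocol gives neither the ICC nor the dyad share that such a claim would need. The allocation wording is minor.

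**What to change.** Reconcile Sections 3.1 and 3.5 in one of two ways.

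1. In Section 3.5, make a single pooled comparison the primary analysis, with dyads treated as clusters, and keep the separate analyses as secondary. In Section 3.1, state the power of 68 for that comparison over a stated range of ICC and dyad share.
2. Keep the separate analyses as primary, and replace the 90% in Section 3.1 with the power of each one over a stated range of split and ICC.

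The first keeps the stated power much closer to 90%. Changing Section 3.1 alone to describe a pooled comparison would not be enough, because Section 3.5 would still not plan one.

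In Section 3.2, name the unit of randomisation as the dyad, or the single participant when taking part alone, and check that Figure 1 agrees.

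The cost is a few sentences and a less favourable stated power. No extra recruitment is needed.
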